### **Post-trial Information**

[figure not shown]
- Live birth rate and neonatal health, including minor/major congenital anomalies, at birth and at 4 weeks after birth

### 3 INVESTIGATIONAL PLAN

#### 3.1 Overall Trial Design

##### 3.1.1 Trial Design Diagram

[figure not shown]
A diagram illustrating the trial period is shown in [Figure 3-1](#).

- GnRH agonist (GONAPEPTYL 0.1 mg/day) from the mid-luteal phase (i.e. day 21-24) of the subject's menstrual cycle and continued throughout the stimulation period.
- The FE 999049 dose is based on the subject's AMH at screening and body weight on stimulation day 1. In the GnRH agonist protocol, stimulation with FE 999049 starts when down-regulation is established. In the GnRH antagonist protocol, stimulation with FE 999049 starts on day 2-3 of the subject's menstrual cycle.
- GnRH antagonist (CETROTIDE 0.25 mg/day) from stimulation day 6 and continued throughout the stimulation period.
- hCG (OVITRELLE 250 µg single dose) when triggering criterion is met.
- Progesterone (LUTINUS 3x100 mg/day) from the day after oocyte retrieval and continued until the day of the βhCG visit. Luteal phase support may be continued after a positive βhCG test is obtained if this is local practice.
- Stimulation day 1, 6 and hereafter at least every second day. When the leading follicle reaches ≥15 mm, visits will be scheduled daily.

**Figure 3-1 Trial Diagram – Trial Period**

A diagram illustrating the post-trial activities is shown in [Figure 3-2](#).

**Figure 3-2 Trial Diagram – Post-trial Activities**

### 3.1.2 Overall Design and Control Methods

#### Trial Design

This will be a randomised, controlled, open label, parallel group, multicentre trial comparing the efficacy and safety of individualised FE 999049 dosing in first cycle patients aged 18-40 years undergoing controlled ovarian stimulation for IVF/ICSI following either a long GnRH agonist protocol or a GnRH antagonist protocol. The trial has been designed to describe potential differences in the mean number of oocytes retrieved with adequate precision.

Subjects will be screened within 90 days prior to randomisation for compliance with the inclusion and exclusion criteria. Randomisation may take place as soon as all eligibility criteria are met. Randomisation does not necessarily need to take place at a physical visit, but can be done by delegated trial staff without the subject being present at the clinic. However, the subject will be contacted prior to randomisation to confirm eligibility. Subjects will be randomised in a 1:1 ratio to controlled ovarian stimulation with FE 999049 in a long GnRH agonist protocol or to controlled ovarian stimulation with FE 999049 in a GnRH antagonist protocol. Randomisation will be stratified by centre and according to age (<35, 35-37 and 38-40 years). The subject will be informed of treatment allocation and when to start treatment by the delegated trial staff.

Subjects randomised to treatment with FE 999049 in the long GnRH agonist protocol will start down-regulation with GnRH agonist (triptorelin acetate, GONAPEPTYL) 0.1 mg/day

subcutaneously in the mid-luteal phase (i.e. cycle day 21-24) of their menstrual cycle. Ovarian stimulation with FE 999049 will start after 14 days ( $\pm 1$  day) if the subject has experienced withdrawal bleeding and the following down-regulation criteria are fulfilled: 1) a thin endometrium ( $<5$  mm) is observed by transvaginal ultrasound, and 2) no ovarian follicles  $\geq 10$  mm (including cysts that cannot be punctured prior to stimulation) are observed by transvaginal ultrasound. In case achievement of down-regulation is doubtful or it is deemed helpful, serum estradiol is to be measured ( $<50$  pg/mL or  $180$  pmol/L; local laboratory). If down-regulation is confirmed and ovarian stimulation is initiated, treatment with GnRH agonist is continued throughout the stimulation period. If the subject has not experienced withdrawal bleeding after 14 days ( $\pm 1$  day), a urinary pregnancy test is to be performed. If the subject is not pregnant and down-regulation is not confirmed, treatment with GnRH agonist will be continued and stimulation will be postponed until down-regulation is confirmed. Subsequent visit(s) for confirmation of down-regulation will be scheduled according to local practice. If down-regulation is not achieved after 28 days, treatment with GnRH agonist will be stopped and the subject will be withdrawn from the trial.

Subjects randomised to treatment with FE 999049 in the GnRH antagonist protocol will start stimulation with FE 999049 on day 2 or 3 of their menstrual cycle. To prevent a premature LH surge, a GnRH antagonist (cetrorelix acetate, CETROTIDE) 0.25 mg/day subcutaneously will be initiated on stimulation day 6 and continued throughout the stimulation period.

Subjects will have their individual FE 999049 dose determined on the basis of their AMH level at screening and their body weight on stimulation day 1. The daily FE 999049 dose will be fixed throughout the stimulation period. For subjects with AMH  $<15$  pmol/L the daily FE 999049 dose is  $12$   $\mu$ g, irrespective of body weight. For subjects with AMH  $\geq 15$  pmol/L the daily FE 999049 dose is on a continuous scale ranging from  $0.19$  to  $0.10$   $\mu$ g/kg, i.e. dependent on actual AMH and body weight. AMH will be measured by Elecsys® AMH Plus Immunoassay (Roche Diagnostics). The maximum allowed daily FE 999049 dose is  $12$   $\mu$ g. Subjects can be treated with FE 999049 for a maximum of 20 days, and coasting is not allowed.

During stimulation, subjects will be monitored by transvaginal ultrasound on stimulation day 1 and 6 and hereafter at least every second day. When the leading follicle reaches  $\geq 15$  mm, visits must be performed daily. Triggering of final follicular maturation will be done as soon as  $\geq 3$  follicles with a diameter  $\geq 17$  mm are observed. If there are  $<25$  follicles with a diameter  $\geq 12$  mm, a single dose of hCG (OVITRELLE)  $250$   $\mu$ g will be administered. If there are  $\geq 25$  follicles with a diameter  $\geq 12$  mm, the cycle will be cancelled. If it is judged by the investigator that  $\geq 3$  follicles with a diameter  $\geq 17$  mm cannot be reached, but 1 or 2 follicles with a diameter  $\geq 17$  mm are observed, the cycle may either be cancelled due to poor follicular development or triggering of final follicular maturation is to be induced, as judged by the investigator.

Oocyte retrieval will take place 36h ( $\pm 2$ h) after triggering of final follicular maturation and the oocytes can be inseminated by IVF and/or ICSI. Fertilisation and embryo development will be assessed from oocyte retrieval to the day of transfer. For all subjects blastocyst transfer is performed on day 5 after oocyte retrieval. Subjects  $<38$  years at randomisation will have single

blastocyst transfer. Subjects  $\geq 38$  years at randomisation will have single blastocyst transfer if they have a good-quality blastocyst available, i.e. a blastocyst of grade 3BB or higher; otherwise they may have double blastocyst transfer. Remaining blastocysts may be cryopreserved and used by the subject after completion of the trial, in accordance with local guidelines and/or regulations. All procedures and assessments related to cryopreserved cycles will take place outside this protocol and will not be paid for by Ferring.

Vaginal progesterone tablets (LUTINUS) 100 mg three times daily will be provided for luteal phase support from the day after oocyte retrieval and until the serum  $\beta$ hCG test. Luteal phase support may be continued after a positive  $\beta$ hCG is obtained if this is local practice. A serum  $\beta$ hCG test is performed 13-15 days after transfer, clinical pregnancy will be confirmed by transvaginal ultrasound 5-6 weeks after transfer, and ongoing pregnancy will be confirmed by transvaginal or abdominal ultrasound 10-11 weeks after transfer.

Blood samples will be collected throughout the trial for the purpose of evaluating the endocrine profile assessed at screening, stimulation day 1, stimulation day 6, end-of-stimulation and at oocyte retrieval.

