The development of FE 999049 has prospectively incorporated the use of a biomarker of ovarian response to gonadotropins (anti-Müllerian hormone [AMH]) to identify patients at higher risk of reduced efficacy or increased safety concern, enabling stratification according to the patients' potential to respond to FE 999049. Furthermore, body weight has been shown to influence the exposure to FE 999049. Therefore, the posology of FE 999049 is individualised for each patient based on her body weight and serum AMH to obtain an ovarian response with favourable safety/efficacy profile. The outcome is a fixed-dose regimen supporting individualised ovarian stimulation with safe and efficient use of FE 999049 founded on current scientific knowledge and prospectively confirmed data.

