#### FE 999049 Dosing Regimen

Subjects will have their individual FE 999049 dose determined on the basis of their AMH level at screening and their body weight on stimulation day 1. For subjects with low AMH (<15 pmol/L) the daily FE 999049 dose is 12 µg, irrespective of body weight. For subjects with high AMH ( $\geq 15$  pmol/L) the daily FE 999049 dose is on a continuous scale ranging from 0.19 to 0.10 µg/kg, i.e. dependent on actual AMH and body weight.

The daily FE 999049 dose will be fixed throughout the stimulation period. The maximum allowed daily FE 999049 dose is 12 µg. Dosing will continue until the criterion for triggering of final follicular maturation has been met. Subjects can be treated with FE 999049 for a maximum of 20 days. Coasting is not allowed. Overdose and medication errors of FE 999049 with and without clinical consequences will be tracked in the e-CRF and reviewed ongoing by Ferring Global Pharmacovigilance.

The complete FE 999049 dosing regimen is tabulated in detail in [Table 5-1](#).

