**Table 5-1 FE 999049 Dosing Regimen**

AMH concentration (pmol/L)	Daily dose fixed throughout stimulation	Maximum daily dose
<15	12 µg	12 µg
15-16	0.19 µg/kg	12 µg
17	0.18 µg/kg	12 µg
18	0.17 µg/kg	12 µg
19-20	0.16 µg/kg	12 µg
21-22	0.15 µg/kg	12 µg
23-24	0.14 µg/kg	12 µg
25-27	0.13 µg/kg	12 µg
28-32	0.12 µg/kg	12 µg
33-39	0.11 µg/kg	12 µg
≥40	0.10 µg/kg	12 µg

AMH concentration will be rounded off to integers. The cut-off limit for AMH in this trial is 35 pmol/L, i.e. only subjects with AMH level  $\leq$  35 pmol/L will be included in the trial.

Subjects can be treated for a maximum of 20 days.

The FE 999049 preparation is administered as daily subcutaneous injection(s) in the abdomen.a To minimise local injection site reactions, it is advisable to change injection site regularly.

The first FE 999049 injection will take place at the clinic and will be performed either by the delegated trial staff or the subject under supervision by the delegated trial staff. Subsequent injections can be done at home or at the clinic. The delegated trial staff will give the subject instructions for how to administer FE 999049.

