## **Circulating Concentrations of FSH, LH, Estradiol, Progesterone and Inhibin B on Stimulation Day 6, End-of-stimulation and at Oocyte Retrieval**

For each parameter, the concentrations on stimulation day 6, end-of-stimulation, and at oocyte retrieval will be described and compared for the long GnRH agonist protocol versus the GnRH antagonist protocol using analysis of variance models with treatment, age stratum, and AMH at screening ( $<15$  pmol/L or  $\geq 15$  pmol/L) as factors. Multiplicative models will be used, i.e. the concentrations will be log-transformed before analysis. The results of the analyses will be back-transformed and presented as estimated geometric means for each parameter, and the mean ratios for long GnRH agonist protocol versus GnRH antagonist protocol with 95% confidence intervals.

The analyses will be based on subjects in the FAS starting treatment with FE 999049, i.e. multiple imputations will not be used (this is the same as using the safety analysis set). Values below the lower limit of quantification (LLOQ) will be estimated with LLOQ/2.

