## **Total Gonadotropin Dose and Number of Stimulation Days**

The total gonadotropin dose and the number of stimulation days will be described for each of the two protocols and for subgroups based on age strata and AMH at screening.

Number of stimulation days, total dose, and the average daily dose will be compared between long GnRH agonist protocol and the GnRH antagonist protocol using an analysis of variance model with treatment, age stratum, and AMH at screening ( $<15$  pmol/L or  $\geq 15$  pmol/L) as factors. This analysis will be based on subjects in the FAS that started treatment with FE 999049, i.e. multiple imputations will not be used (this is the same as using the safety analysis set).

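### The total-dose and FSH comparisons in SAP 10.3 leave out baseline weight and finer AMH, which largely determine the assigned dose above 15 pmol/L; adding them would narrow the total-dose interval at almost no cost

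*Protocol*

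**What the plan says.** Protocol 3.1.2 bases the dose on "their AMH level at screening and their body weight on stimulation day 1" and then holds it constant: "The daily FE 999049 dose will be fixed throughout the stimulation period". Both arms use the same algorithm (Protocol 5.1.1 and Table 5-1). "For subjects with low AMH (<15 pmol/L) the daily FE 999049 dose is 12" µg, whatever the weight. From 15 pmol/L up to the trial's ceiling of 35, Table 5-1 steps down from 0.19 to 0.11 µg/kg, with a 12 µg cap.

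On analysis, SAP 10.3 (Total Gonadotropin Dose and Number of Stimulation Days) says: "Number of stimulation days, total dose, and the average daily dose will be compared between long GnRH agonist protocol" and the antagonist protocol. The model is an analysis of variance with treatment, age stratum and two-level AMH, in women who started FE 999049. The hormone concentrations, FSH among them, are log-transformed and compared "using analysis of variance models with treatment, age stratum, and AMH at screening", again at two levels. The dose comparisons are additions listed in SAP section 14; Protocol 9.6.3 only describes total dose and days. Protocol 1.1 notes that "body weight has been shown to influence the exposure to FE 999049".

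**The concern.** Total dose is daily dose times days. The days may respond to the GnRH protocol; the daily dose is essentially settled before the first injection by quantities that treatment hardly affects. Variation in assigned dose that the model does not explain is therefore removable noise in the total-dose comparison. For FSH, exposure per kilogram varies even where the dose is constant, because below 15 pmol/L women of different weights all receive 12 µg.

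The trial is justified by precision of estimation, with no hypothesis test (SAP 4.2 and 10.1). Both endpoints are named secondary endpoints, and Protocol 1.2 expects about one extra day of dosing in the agonist arm. What is at stake is the width of these secondary intervals and how the average-daily-dose line is read.

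**Working it through.** **The plan's own precision figure.** The only one given is for oocytes: 1.96 × 7.0 × √(2/200) = 1.37, which rounds to the stated ±1.4. No precision is stated for dose or FSH. The same formula, half-width = 1.96 × residual SD × √(2/200) = 0.196 × residual SD, is used below.

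**How far dose varies within the AMH factor.**
- Below 15 pmol/L: 12 µg for everyone, so no variation in dose. Dose per kg does vary: for illustration, 12/50 = 0.24 µg/kg at 50 kg and 12/80 = 0.15 µg/kg at 80 kg.
- At 15–16 pmol/L: 0.19 µg/kg reaches the cap at 12/0.19 = 63 kg.
- At 33–35 pmol/L: 0.11 × 64 = 7.0 µg at 64 kg, and 0.11 × 45 = 5.0 µg at 45 kg.

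So the upper stratum spans roughly 5 to 12 µg. In simulations of Table 5-1 (AMH rounded to integers, 0.33 µg pen steps, 12 µg cap), two-level AMH explains about 41–57% of the variance in assigned dose and leaves a residual SD of about 1.1–1.4 µg/day.

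**Total dose, central case.** Assumptions not in the documents: 50% with AMH ≥15; weight about 65 kg, SD 10; mean 8.9 days (antagonist) and 9.9 (agonist), so 9.4 overall; SD of days 2.0. (The ESTHER-1 means in Protocol 1.1 imply (9.6 − 7.5)/(11.2 − 7.5) = 57% with AMH ≥15, but without this trial's ceiling of 35.) The simulated mean dose is 9.74 µg in the upper stratum and the residual dose SD is 1.25 µg.
- Variance from unexplained dose: 9.4² × 1.25² ≈ 138.
- Variance from days: the mean dose is (12 + 9.74)/2 = 10.87; the mean squared dose is 10.87² + 1.25² + (12 − 9.74)²/4 ≈ 121; times 2.0² ≈ 484.
- Planned model: √(138 + 484) = 24.9 µg, half-width 0.196 × 24.9 = 4.9 µg.
- With assigned dose in the model: √484 = 22.0 µg, half-width 0.196 × 22.0 = 4.3 µg.
- Variance removed: 138/622 = 22%.

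The simulated values agree (SD 24.9 to 22.0). Using the dose computed from screening weight, with 40–60% at AMH ≥15, weight about 64 kg (SD 9–11) and SD of days 1.5–2.5, the variance removed is about 13–43%. The expected difference, one more day of dosing, is about 10–11 µg.

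**FSH.** If log FSH follows log(dose/kg) with slope b, other log-SD s, and residual SD τ of log(dose/kg) after the AMH factor, the share of variance removed is b²τ²/(b²τ² + s²). In the central case the simulated log-FSH SD is 0.291 with s = 0.25 and b = 1, so τ² = 0.291² − 0.25² = 0.022.
- b = 0.5, s = 0.5: 0.0055/0.2555 = 2%.
- b = 1, s = 0.2: 0.022/0.062 = 35%.

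Across the wider weight and AMH assumptions the range is about 2–42%. Assigned dose in µg alone removes only 2–8%, because dose is constant below 15 pmol/L while weight is not. The useful term is weight, or dose per kg.

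**Average daily dose.** The chance half-width under the planned model is 0.196 × (1.1 to 1.4) ≈ 0.22–0.27 µg. In simulation, a systematic between-arm weight shift of 0.5, 1 or 2 kg on stimulation day 1 moves mean daily dose by about 0.03, 0.06 or 0.12 µg.

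**The case against.** The planned estimates are unbiased and their intervals valid. The trial was sized on oocytes, and no precision target exists for dose. With an expected difference of about 10–11 µg, a half-width of 4.9 or 4.3 µg answers the question about equally well. All of this stands. The gain can be expressed as extra women, (4.9/4.3)² ≈ 1.30 or about 120 on 400, but that should not be read as a shortfall in the design.

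Three stronger readings are tempting, and the documents support none of them.
- A reader might infer that the models ignore assigned dose. They do not: the AMH factor is split at the dosing threshold and fixes the dose exactly below it.
- A reader might infer that average daily dose can differ between arms only by chance. Dosing weight is measured after randomisation, and in the agonist arm after roughly two to four weeks of down-regulation. The analysis includes only women who started FE 999049; Protocol 3.5.1 foresees different withdrawal patterns, and failed down-regulation (Protocol 4.4) can remove women from the agonist arm only. Incorrect doses are also recorded (Protocol 5.6.2). Small systematic differences are possible, so the comparison need not be dropped. That its interval would exclude zero in about 5% of trials with no true difference is what any valid 95% interval does.
- A reader might treat dose as the main determinant of circulating FSH. Protocol 1.1 says only that weight influences exposure. The slopes and SDs used above are assumed, and the relation may differ at oocyte retrieval, after stimulation has ended.

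**Conclusion.** The point holds as a modest precision refinement. The total-dose model omits baseline information that would remove about 13–43% of its residual variance, with a central half-width falling from about 4.9 to 4.3 µg. That size depends on the assumed AMH mix, weight distribution and SD of stimulation days. For FSH the direction is plausible, but the size rests on an assumed exposure relation and may be negligible. Average daily dose says almost nothing about an effect of the GnRH protocol, because the shared algorithm leaves it little room; it remains useful as a check of balance and adherence. There is no bias, and neither the primary endpoint nor the sample size is affected.

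**What to change.** In SAP 10.3, keeping the existing factors:
1. **Total dose.** Add as a covariate the algorithm daily dose computed from screening AMH and screening weight, with the Table 5-1 rounding and cap. Use screening weight, not day-1 weight, so that the covariate precedes randomisation.
2. **FSH.** Add log(algorithm dose per kg screening weight), or screening weight. State that the gain is uncertain and may differ at oocyte retrieval.
3. **Average daily dose.** It may stay in the report, with a sentence saying that it is read as a check of balance and adherence, and that day-1 weight, withdrawal before start or dosing errors could shift it slightly.

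The cost is SAP wording and one or two derived variables. Screening AMH and weight are already collected (Protocol 6.2), and the algorithm is already programmed in the e-CRF (Protocol 5.1.1). Item 1 modifies an analysis that the SAP itself added. Item 2 extends a model whose factors are named in Protocol 9.6.3, so it should be listed in SAP section 14 or run as a supplementary analysis. As the trial is open label, the change should be fixed before the comparative data are examined.

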### **Post-trial Activities**

Post-trial activities cover pregnancy and neonatal health follow-up. All subjects with an ongoing pregnancy will be followed till delivery to gather information on live birth rate. Furthermore, data will be gathered on neonatal health, including minor/major congenital anomalies, at birth and at 4 weeks after birth. These data will be reported separately.

#### **3.1.3 Trial Schedule**

First patient first visit (FPFV):	Q1 2019
Last patient first visit (LPFV):	Q3 2021
Last patient last visit (LPLV) / end-of-trial:	Q1 2022
Post-trial follow-up completed:	Q4 2022

#### **3.2 Planned Number of Trial Sites and Subjects**

It is planned to randomise approximately 400 subjects from approximately 15 sites. Approximately 200 will be randomised to the long GnRH agonist protocol and approximately 200 will be randomised to the GnRH antagonist protocol. It is estimated that up to 500 subjects should be screened to achieve 400 randomised and treated subjects.

### **3.3 Interim Analysis**

No interim analysis is planned.

### **3.4 Data Monitoring Committee**

No Data Monitoring Committee will be established for this trial.

## **3.5 Discussion of Overall Trial Design and Choice of Control Groups**

### **3.5.1 Trial Design**

The primary objective of the trial is to evaluate the effect of individualised FE 999049 treatment on ovarian response in a long GnRH agonist protocol versus a GnRH antagonist protocol.

This is a randomised controlled trial with a parallel group design which is preferred over a cross-over design in fertility trials. The trial will be open label as a double-blind design is not feasible due to the required GnRH agonist treatment prior to start of stimulation in a long GnRH agonist protocol. In contrast, in a GnRH antagonist protocol, the GnRH antagonist is only started during the mid-follicular phase of the stimulation period. Prior to start of stimulation in a long GnRH agonist protocol, down-regulation needs to be confirmed based on ultrasound findings, thus neither patients nor the assessors in this trial can be blinded. The lack of blinding may result in different withdrawal patterns for the two protocols. To minimise this, only subjects without strong preference for one of the protocols will be included. The trial will be a multicentre, multinational trial. This set-up ensures that the required number of subjects can be recruited within a reasonable time and also has the advantage that it should facilitate subsequent generalisation of the results.

Randomisation will be stratified by age group (<35, 35-37 and 38-40 years). Age is known to influence ovarian response, e.g. the primary endpoint, number of oocytes retrieved, as well as pregnancy endpoints such as clinical pregnancy rate and ongoing pregnancy rate. Stratification by age group will ensure that within each age group, a similar number of subjects is randomised to each protocol. This will increase the precision of the trial and facilitate separate presentations by age group. In addition, randomisation is stratified by centre as ovarian response and pregnancy outcome may differ between centres.

Subjects will undergo controlled ovarian stimulation with an individualised dosing regimen of FE 999049 based on the subject's AMH level and body weight, following either a long GnRH agonist protocol or a GnRH antagonist protocol. The daily FE 999049 dose is fixed throughout the stimulation period in this trial. The selection of doses is described in detail in section [3.5.4](#). Monitoring of ovarian response by transvaginal ultrasound and blood sampling for assessment of several endocrine parameters will be performed regularly during stimulation.

In this trial, subjects with  $\geq 25$  follicles of  $\geq 12$  mm at end of stimulation will be cancelled, meaning that hCG will be withheld in both treatment groups. Subjects in the GnRH antagonist group with

such high ovarian response could in principle receive GnRH agonist for triggering of final follicular maturation, but this approach is not allowed as an identical cancellation policy for both treatment groups is essential for a valid comparative analysis of the primary endpoint. However, the anticipated number of subjects that needs to be cancelled in the current trial is anticipated to be low. In the previous phase 3 trial ESTHER-1, there was no upper cut-off level for AMH, and only 2.5% of all subjects had  $\geq 25$  follicles  $\geq 12$  mm at the end of stimulation. The incidence was only 1.2% for FE 999049 treated subjects with AMH  $\leq 35$  pmol/L. In this phase 3b trial, subjects with AMH  $> 35$  pmol/L will be excluded which will lower the frequency of potential high responders, such as subjects with polycystic ovarian syndrome (PCOS) who have an increased risk of developing OHSS. Based on the incidence of 1.2% in the ESTHER-1 trial, only 5 subjects of the planned 400 randomised subjects are expected to be cancelled due to this criterion.

Oocytes will be inseminated by either IVF or ICSI reflecting the procedures used in the target population for the proposed indication. Embryos will be cultured for 5 days and embryo development will be assessed from oocyte retrieval till the day of transfer, allowing evaluation of embryo development until blastocyst stage.

The present protocol requires single blastocyst transfer on day 5 for all women  $< 38$  years and for women  $\geq 38$  years with at least one good-quality blastocyst available. Women  $\geq 38$  years with no good-quality blastocyst may have double blastocyst transfer. The scientific justification for incorporating these features is that it will ensure that the data obtained in this trial are in line with the current clinical directions taken for maintaining efficacy (i.e. ongoing pregnancy rates) and minimising risks (i.e. multiple pregnancies). Further, there is increasing evidence suggesting that late stages of embryo progression are better predictors of clinical pregnancy than early embryo development parameters. In good prognosis patients, the transfer of blastocysts yields a higher live birth rate than that achieved with transfer of the same number of cleavage stage embryos.

Subjects who achieve an ongoing pregnancy will be followed till live birth to collect information on pregnancy outcome. In addition, neonatal health data will be gathered at birth and at 4 weeks after birth.

